3.4 Study Plan

3.4.1 Schedule

The previously vaccinated cohort receives the vaccine boost once every six months (+/- 30 days). As of Amendment #9, participants will be switched to annual vaccinations (+/- 30 days).

The vaccine naïve cohort receives the priming vaccine once every month (+/- 3 days) for three months, then a vaccine boost every six months (+/-30 days) beginning six months after prime vaccine #3. As of Amendment #9, participants will be switched to annual vaccinations (+/- 30 days).

At any time during the study additional leukapheresis or approximately 200 cc of blood may be obtained, and skin biopsies and photos may be taken of the vaccine sites and rashes, as clinical indicated, as long as the research participant is in agreement.

All research participants will be seen in the oncology outpatient center for vaccine administration and monitoring. Research participants will be monitored for at least 30 minutes following vaccination for evidence of acute reaction to the injected vaccine cells.

Research participants and the study team may request additional optional study visits for discussions and evaluations. During these patient-requested or clinically-indicated visits, additional assessments may be obtained, including, but not limited to a history and physical examination, toxicity assessment, vital signs, skin biopsy, photos, imaging tests, and clinical laboratory testing.

3.4.1.1.Both Cohorts- Vaccination #1:

This is the Prime Vaccination #1 for Vaccine Naïve Cohort and the Boost Vaccination #1 for Previously Vaccinated Cohort.

Baseline data and samples (May be obtained from Day-28 to Day 0)

1. A clinical evaluation to include vital signs, ECOG status, weight, review of systems, physical examination, and toxicity evaluation.
2. CT scans of the abdomen, pelvis, and chest. If the CT scan is not done at Hopkins, the research participant must provide the report and a copy of the scans. If the research participant is allergic to the CT scan contrast or the contrast is contraindicated (as in the case for renal insufficiency), a non-contrast CT of the chest and a MRI of the abdomen and pelvis will be obtained.

3. A leukapheresis for in vitro studies will be encouraged. If the research participant refuses a leukapheresis, approximately 200 cc of blood will be drawn.

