The sample size was expanded to include a cohort of up to 45 vaccine-naïve research participants and 17 previously vaccinated research participants for a total sample up to 62 research participants.

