4.3 Analysis of Secondary Endpoints

The analysis of the remaining endpoints are primarily descriptive in nature and are intended to be used to generate estimates of efficacy and hypotheses to be tested in later trials. For each endpoint, separate analyses will be performed for the vaccine naïve and vaccine treated patients.

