We are also interested in investigating the effect of vaccine boosts on recurrence free survival (PFS). Patients who are treated at Johns Hopkins will be followed every 3 months and evaluated for recurrence. However, the standard of care follow-up varies from institution to institution. In order to prevent biasing our results, it is necessary to coarsen the follow-up interval so that every individual is evaluated at the same time points regardless of the institution. For example, if the only visits held in common among all patients were the semi-annual exams prior to vaccine boosting, it would be necessary to only consider the status of the JH patients at those two time points regardless of recurrence information gained from the additional 2 visits. This coarsening of the data may cause an overestimation of PFS. In order to take into account both potential forms of bias, we will perform our analysis of PFS on the entire cohort as well as the subpopulation of patients from Johns Hopkins (estimated to be approximately 50% of the research participants). PFS will be defined as the time from the first vaccine until evidence of disease recurrence. If a patient withdraws from the study prior to being diagnosed with progressive disease, they will be censored at the date of their last follow-up visit. If an individual dies prior to being diagnosed with progressive disease, they will be considered to have progressed at the date of their last follow-up visit. This is a conservative estimate if we count the disease recurrence at the next planned visit then this will bias the PFS time upward. The PFS will be summarized using Kaplan-Meier curves and estimates of median PFS with 95% confidence intervals based upon Greenwood's formula. Due to potential causes of bias discussed earlier, the results will be considered extremely preliminary. If the PFS estimates for patients treated at Johns Hopkins appear to be lower than that of the population as a whole and the Johns Hopkins patients are followed at more frequent intervals than the other patients, then this indicate that an overestimation of PFS may exist. No formal comparison is planned due to the small sample size. Such results could affect the future planning of follow-up treatment for patients in subsequent trials.

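### The planned check for overestimated PFS, Johns Hopkins against the whole cohort, mixes coarsening with institution and is noisy; scoring the same Johns Hopkins patients on both schedules would measure coarsening directly

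*Combined protocol and SAP*

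**What the plan says.** Section 4.3.1 of the combined protocol and SAP notes that follow-up differs by institution: "Patients who are treated at Johns Hopkins will be followed every 3 months and evaluated for recurrence", while other centres follow their own practice. It therefore reduces everyone to shared time points. Its example is the case where "the only visits held in common among all patients were the semi-annual exams prior to vaccine boosting". It names the price: "This coarsening of the data may cause an overestimation of PFS".

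To address this, PFS is to be analysed in the entire cohort and in the "subpopulation of patients from Johns Hopkins (estimated to be approximately 50% of the research participants"). The interpretive rule begins "If the PFS estimates for patients treated at Johns Hopkins appear to be lower than that of the population as a whole". It has a second condition, that Johns Hopkins patients are followed more often than the others. If both hold, the plan reads this as a sign that PFS may be overestimated. No formal comparison is planned, and the results are described as highly preliminary, but the section adds that they could influence follow-up in later trials.

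Three other provisions matter:

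- Section 4.3 splits the analysis by cohort: "For each endpoint, separate analyses will be performed for the vaccine naïve and vaccine treated patients".
- Section 4.1 sets the sizes: "The sample size was expanded to include a cohort of up to 45 vaccine-naïve research participants and 17 previously vaccinated research participants".
- Section 3.4.1 lengthens the boost interval: "As of Amendment #9, participants will be switched to annual vaccinations (+/- 30 days").

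Section 4.3.1 also dates a death before diagnosed recurrence back to the last follow-up visit.

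**The concern.** The effect to be detected is the shift in PFS when the same recurrences are dated on a coarser grid. The planned contrast sets Johns Hopkins patients on their own schedule against a population made up partly of patients treated and followed elsewhere. Any real difference in prognosis between institutions enters alongside the coarsening shift. Section 3.2.2 leaves treatment around surgery to local oncologists, so such a difference is plausible, although the documents report none. The second condition does not remove it: more frequent follow-up at Johns Hopkins is what the plan expects anyway, so the condition will usually be met whatever the case mix.

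At stake is the interpretation of a descriptive secondary endpoint and the follow-up lesson drawn from it. A case-mix difference could be attributed to visit frequency, or could hide a real coarsening effect. Nothing in the primary safety analysis is affected.

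**Working it through.** **The plan's own figure.** The documents give no number for this check and no assumed PFS for this trial. Everything below rests on stated assumptions.

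**Inputs from the documents.** Johns Hopkins share about 50% (4.3.1), so 45 × 0.5 ≈ 22 vaccine-naïve and 17 × 0.5 ≈ 8 previously vaccinated patients, if the share is the same in both cohorts. Johns Hopkins interval 3 months. Common grid 6 months in the plan's example, or 12 months if boost examinations are the only shared visits after Amendment #9.

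**Assumed.** Exponential time to recurrence, detection at the next visit, complete follow-up to 36 months, no deaths before detection.

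**Formula.** With median m, λ = ln 2 / m and visits every k months, the expected 36-month restricted mean is

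E(k) = k × (1 − e^(−36λ)) / (1 − e^(−kλ)).

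| Median (months) | E(3) | E(6) | E(12) |
|---|---|---|---|
| 10 | 14.66 | 16.18 | 19.50 |
| 14 | 18.08 | 19.42 | 22.28 |
| 20 | 21.66 | 22.78 | 25.14 |

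For m = 14: λ = 0.0495 and 1 − e^(−1.782) = 0.832. So E(3) = 3 × 0.832 / 0.138 = 18.08 and E(6) = 6 × 0.832 / 0.257 = 19.42.

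**Two contrasts.** Within-patient: Johns Hopkins E(k) − E(3). Plan's check: whole cohort on the common grid, (22 × Hopkins E(k) + 23 × other E(k)) / 45, minus Hopkins E(3). A positive value is the direction the plan looks for.

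| Hopkins / other median | Grid | Plan's check | Within-patient |
|---|---|---|---|
| 14 / 14 | 6 | 19.42 − 18.08 = 1.34 | 1.34 |
| 14 / 14 | 12 | 22.28 − 18.08 = 4.20 | 4.20 |
| 20 / 14 | 6 | 21.06 − 21.66 = −0.6 | 1.12 |
| 20 / 14 | 12 | 23.68 − 21.66 = 2.02 | 3.48 |
| 10 / 14 | 6 | 17.84 − 14.66 = 3.18 | 1.52 |
| 10 / 14 | 12 | 20.92 − 14.66 = 6.26 | 4.84 |

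With Hopkins patients doing worse, the planned contrast overstates the shift by 3.18 / 1.52 = 2.1 times on the 6-month grid and 6.26 / 4.84 = 1.3 times on the annual grid.

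**Noise (simulation, 22 of 45 at Johns Hopkins).** Equal 14-month medians, 6-month grid: the plan's contrast has SD about 1.83 and the wrong sign in 23–24% of trials, in line with Φ(−1.34 / 1.83) = Φ(−0.73) = 0.23. The within-patient contrast has SD 0.32. On the annual grid the plan's contrast has the wrong sign in about 1%. With 20 against 14 months it is wrong in about 62% (6-month) and 15% (annual).

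**Other settings.**

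- Previously vaccinated cohort (n = 17), equal hazards, 6-month grid: restricted-mean sign wrong in 30–35%.
- Medians, which the plan reports: with 40–45 naïve patients, equal hazards, a 6-month grid and assumed medians of 10 to 24 months, the Johns Hopkins median is lower in 52–60% of runs, tied in 23–35% and higher in 9–23%.
- The paired median also ties in about half of runs on a 6-month grid.

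**Death rule.** Suppose recurrence is seen at month 9 and death follows at month 11. The 3-monthly record gives month 9. If the interim finding is ignored on a 6-month grid, the patient counts as dead before diagnosis and is dated to month 6; assigned to the next common visit, the date is month 12. With the rule applied literally on the coarse grid (18-month median PFS, 20 Johns Hopkins patients), the within-patient shift for assumed post-recurrence medians of 12, 6 and 3 months is +0.67, +0.27 and −0.30 months on the 6-month grid, and +1.21, −0.34 and −1.90 on the 12-month grid.

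**The case against.** The best defence is that the plan claims little. Secondary analyses are descriptive, no test is planned, the rule says only that overestimation may exist, and the results are labelled preliminary. That stands, and it limits this point to an inexpensive improvement.

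A reader might also infer four stronger criticisms that do not hold:

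- *The overlap dilutes the signal.* If the whole cohort is coarsened as Section 4.3.1 describes, the Johns Hopkins patients within it carry coarsened dates, and with equal hazards the mean shift is the same as within patients (1.34 in both). The overlap even helps: with 40 patients and a 10-month median on a 6-month grid, the sign is right in 80.5% of runs, against 68.3% for Johns Hopkins against non-Hopkins. Dilution would arise only if the whole cohort were left uncoarsened.
- *The check usually points the wrong way.* That needs an assumed Johns Hopkins advantage and a 6-month grid. With equal hazards, failing to show the bias, often through tied medians, is commoner than reversal.
- *The plan takes a Johns Hopkins PFS that is not lower as proof of no bias.* It does not; the rule runs in one direction only.
- *The within-patient check cannot go wrong.* Without deaths its sign is fixed by construction, so it informs on size rather than direction. Under the literal death rule it can turn negative.

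One further caution stands. Section 4.3.1 promises 3-monthly evaluation for recurrence at Johns Hopkins and Section 3.4.4 at least quarterly record review, but Section 5.1 defines recurrence by CT, and interim scans are permitted rather than required. The finer curve can be no better than the evaluations actually made.

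**Conclusion.** The point holds as a cheap improvement to a descriptive secondary analysis. The planned comparison cannot separate coarsening from a difference between institutions, and it is imprecise at this size: mean about 1.3 months, SD about 1.8, on a 6-month grid with equal prognosis, against SD 0.32 for the paired contrast. Reversal then occurs in about a quarter of trials, but in only about 1% on an annual grid. A true Johns Hopkins advantage can mask the effect, and a disadvantage can inflate it.

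These sizes depend on exponential recurrence, the assumed medians, 36 months of complete follow-up, an even Johns Hopkins share and no deaths before diagnosis. The institutional differences are illustrations, since the documents supply none. Whether the common grid is now 6 months, 12 months or a mixture is also not settled by Section 4.3.1, whose example remains semi-annual.

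**What to change.** Amend Section 4.3.1 as follows:

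1. Judge the coarsening effect within Johns Hopkins patients. Compute their PFS once from all 3-monthly evaluations and once on the common grid. Report both curves and the restricted-mean difference, by cohort, because medians often tie.
2. State the common grid in force after Amendment #9.
3. State how death before diagnosis is handled on each grid. A recurrence already seen at an interim visit should be assigned to the next common visit, including when the patient has left the study or died before it, and not dated back to the previous one. Show the result with and without the death rule.
4. Keep a comparison of Johns Hopkins with non-Hopkins patients, both on the common grid, only as a description of case mix.

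The cost is wording and a little more analysis of follow-up already planned. The limitation is that the result measures coarsening in Johns Hopkins patients only.

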1.0 Study Synopsis

Objectives:

Primary:

1. To evaluate the safety of primary and boost vaccinations with lethally irradiated allogeneic pancreatic tumor cells transfected with the GM-CSF gene vaccine in the treatment of patients with surgically resected adenocarcinoma of the head, neck, or uncinate of the pancreas

Secondary:

1. To estimate the association of specific *in vivo* parameters of immune response including, but not limited to mesothelin, prostate stem cell antigen (PSCA), and mutated *k-ras*-specific T cell responses, with clinical responses in patients who are receiving semi-annual vaccine boosting with lethally irradiated allogeneic pancreatic tumor cells transfected with the GM-CSF gene.
2. To estimate the efficacy of vaccine boosts in the treatment of patients with adenocarcinoma of the pancreas in terms of overall and recurrence free survival.
3. To use the serum GM-CSF levels as a measure of longevity of an allogeneic vaccine following a semi-annual boosting with lethally irradiated allogeneic pancreatic tumor cells transfected with the GM-CSF gene.
4. To determine the psychosocial and symptom profiles of patients with pancreatic cancer treated with an irradiated allogeneic GM-CSF secreting vaccine, and to explore changes over time. The psychosocial profile will include information about, but is not limited to demographics, quality of life, hope, trust, social support, decision control and advanced directives. The symptom profile will include but is not limited to pain, anorexia, fatigue, and mood state.

Study population:

In order to be considered for this study, patients need to meet following major criteria for inclusion: History of surgically resected pathologic stage 1 (no direct tumor extension beyond pancreas and no regional lymph node metastases), 2 (direct extension of tumor beyond pancreas), and/or 3 (regional lymph node metastases) adenocarcinoma of the head, neck, tail, or uncinate of the pancreas.

Have no radiographic evidence of pancreatic cancer disease recurrence.

Have not received any anti-cancer therapy in the past 28 days.

Study Design:

Eligible subjects will receive by intradermal administration the pancreatic tumor vaccine consisting of two irradiated, allogeneic pancreatic tumor cell lines transfected with the granulocyte macrophage-colony stimulating factor (GM-CSF) gene. There will be two cohorts of research participants: those who have previously received the pancreatic cancer vaccine (up to 17) and those

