3.0 Study Design and Treatment Plan

3.1 Trial Overview

This vaccine boost trial will evaluate an equal mixture of two allogeneic GM-CSF secreting pancreatic vaccine cell lines Panc 10.05 and Panc 6.03 for: (1) safety of administration, (2) induction of antitumor immune responses, and (3) disease-free and overall survival in patients with resected adenocarcinoma of the head, neck, tail, or uncinate of the pancreas. Candidates for this study have either: 1) previously been treated at Johns Hopkins with the allogeneic GM-CSF secreting pancreatic cell lines Panc 10.05 and Panc 6.03 per protocol application number 96-01-25-01 entitled "A Phase I Clinical Trial of Lethally Irradiated Allogeneic Pancreatic Tumor Cells Transfected with the GM-CSF Gene for the Treatment of Adenocarcinoma of the Pancreas", SKCCC J9617, or protocol application number 00-01-13-02, entitled "A Safety and Efficacy Trial of Lethally Irradiated Allogeneic Pancreatic Tumor Cells Transfected with the GM-CSF Gene in Combination with Adjuvant Chemoradiotherapy for the Treatment of Adenocarcinoma of the Pancreas", SKCCC J9988; or, 2) received other adjuvant chemoradiation and are now interested in participating in a vaccine study. All patients must meet the eligibility criteria including having no radiographic evidence of disease recurrence at the first vaccination and every semi-annual vaccination. As of Amendment #9, participants will be switched to annual vaccinations.

In this study research participants will receive 5×10^8 cells of a equal mixture of two allogeneic GM-CSF secreting pancreatic vaccine cell lines Panc 10.05 and Panc 6.03 divided into six intradermal injections every year until there is radiographic evidence of disease recurrence, toxicities occur, or the vaccine supply is exhausted. This is the same dose found to be safe and to induce immune responses in the phase I study, and has been shown to be safe in the follow-up of 60 patients in the phase II study. For research participants who had previously received the pancreatic cancer vaccine, one of the semi- annual vaccination boost dates will be the same as the annual follow-up date per protocol application number NA_00036444 (SKCCC J0248), entitled "Long term follow-up of patients who received lethally irradiated pancreatic tumor cells transfected with

the GM-CSF gene.” Assessments and tests included in the long term follow-up will not be duplicated if included in this protocol.

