4.0 Statistical Considerations

4.1 Sample Size

The primary statistical endpoint of this study is to evaluate the safety and feasibility of vaccine boosting with lethally irradiated allogeneic pancreatic tumor cells transfected with the GM-CSF gene. Among patients who have previously been treated with the vaccine, the cohort is limited to those who continue to have no disease recurrence for at least 1 year after treatment. Currently, there are three potentially eligible patients from the original phase I study, and 14 from the phase II study. A total of up to 17 previously treated patients will be eligible to continue to receive vaccine treatment in the form of semi-annual boosts. The second cohort of vaccine naïve patients who have been recurrence free for at least 28 days following adjuvant therapy will be given three priming vaccines each a month apart, followed by semi-annual vaccine boosts in order to determine the feasibility of administering the vaccination to vaccine naïve patients and to obtain initial estimates of the efficacy of such treatment with respect to prolonging disease-free status. As of Amendment #9, participants will be switched to annual vaccinations. We will base our determination of feasibility by estimating the proportion of patients with a dose limiting toxicity (DLT) within 28 days of the first vaccine treatment. Between 20 and 45 vaccine naïve patients will be included. An initial group of 20 patients will be recruited and an interim analysis will be performed in order to guard against excessive toxicities relating to treatment. No DLTs have been observed in either the phase I or II studies. If there is significant evidence that more than 10% of the vaccine naïve patients have dose limiting toxicities within 28 days of the first vaccination, then the trial will be halted. If 6 out of 20 of the initial patients have DLTs, the lower bound of the exact 95% confidence interval for the proportion of patients with a DLT is 11.89%. Therefore, we will halt the trial due to excessive toxicity at the interim analysis if 6 or more patients have a DLT within the first 28 days of their first vaccine. Otherwise, an additional 20 vaccine naïve patients will be accrued. If 20 patients are accrued, the maximum width of the 95% confidence interval estimate of the proportion of patients with a DLT is 0.438. If the full cohort of 40 patients is accrued, then the maximum width of the 95% confidence interval is 0.309.

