Measurements of immune response include but are not limited to mesothelin, prostate stem cell antigen (PSCA) and mutated k-ras-specific T cell responses. Continuous variables will be summarized with means and standard deviations. Dichotomous and categorical variables will be

summarized using proportions with exact 95% confidence intervals and counts, respectively. These summaries will be computed for each patient at two time points around each vaccine boost: pre-vaccination and four weeks post vaccination. Plot will be used to show the changes in immune response over time both for each individual and for each cohort. For each vaccine boost, comparisons in the pre and post-vaccine responses will be compared using paired t-tests (or Wilcoxon signed rank tests if appropriate) for continuous variables and Fisher's exact test for dichotomous or categorical variables. Associations between immune responses will be explored graphically (e.g. scatterplots, boxplots) and numerically (e.g. correlations, χ^2 tests).

Measurements of antitumor immunity include but are not limited to the measurement of shared tumor-specific antigens and k-ras specific antitumor immune responses. Autologous lymphocytes will be obtained from peripheral blood before each vaccination, and at four weeks following each vaccinations. The graphical and numerical analyses of these results will be the same as that described for measurements of immune responses and will be carried out for each cohort separately.

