4.3.2 Relating immune response to clinical response

The relationships between immune and clinical responses will be assessed using a variety of statistical techniques. Preliminary explorations will be graphical in nature (e.g. boxplots, scatterplots). Univariate and multivariate modeling will be used quantify the associations. In the case of a binary clinical outcome (e.g. toxicity), logistic regression will be used. In the case of a time-to-event clinical outcome (e.g. OS), the Cox proportional hazards model will be used.

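### Dichotomous and categorical immune responses before and after a boost, in the same patients, are to be compared with Fisher's exact test, which ignores the pairing

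*Combined protocol and SAP*

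**What the plan says.** The rule is in section 4.3.1 of the combined protocol and SAP, in the part on immune response measurements. On timing it states: "These summaries will be computed for each patient at two time points around each vaccine boost: pre-vaccination and four weeks post vaccination". For each boost, the pre and post responses are then compared with "paired t-tests (or Wilcoxon signed rank tests if appropriate) for continuous variables and Fisher's exact test for dichotomous or categorical variables". Neither test is offered as an example, although the next sentence of the section does give its methods for associations as examples.

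For description, dichotomous and categorical variables are "summarized using proportions with exact 95% confidence intervals and counts, respectively". That gives an interval for the proportion at each time point, but none for the change between them.

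The next paragraph of 4.3.1, on antitumor immunity, has lymphocytes drawn before and four weeks after each vaccination and carries the same methods over: "The graphical and numerical analyses of these results will be the same as that described for measurements of immune responses". No paired test for categorical data is named anywhere in the document.

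**The concern.** Both measurements come from the same patient, so the information about change lies in the patients who switch status. Fisher's test can be run in two ways and neither suits the question.

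- **Pre versus post as two groups.** This is the natural reading. It counts n patients as 2n independent ones. With positive within-patient correlation it rejects too rarely, so a real rise after a boost can be missed. With negative correlation it can reject too often.
- **Pre-by-post cross-table.** This asks whether post status depends on pre status, which is not change.

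Section 3.1 lists "induction of antitumor immune responses" among the things the trial evaluates. For any immune measure coded as responder or non-responder, this is the test the plan assigns to it. Section 4.3 says the secondary results are meant to generate hypotheses for later trials, and a test that misses real rises works against that.

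**Working it through.** **Figure to reproduce.** There is none: the plan states no power, response rate or correlation for this comparison.

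**Inputs from the document.** Section 4.1 gives the previously vaccinated cohort: "A total of up to 17 previously treated patients will be eligible to continue to receive vaccine treatment", so n = 17 at most. It also gives 40 as the full vaccine-naïve cohort (later expanded to 45). Cohorts are analysed separately (4.3). Forty pairs is optimistic: boosts in the naïve cohort start six months after the third prime (3.4.1), patients leave at recurrence (3.4.6), and research bloods at boosts have not been required since Amendment #8 (3.4.1.4).

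**Assumed.** Two-sided 5% level; response rates; within-patient correlation φ of 0, 0.3 and 0.5; n = 25 and n = 12 to represent attrition.

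**Step 1: cell probabilities.** With p1 responders before and p2 after,

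P(positive both times) = p1·p2 + φ·√(p1(1−p1)p2(1−p2)).

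For 20% to 40% at φ = 0.5: 0.08 + 0.5 × 0.196 = 0.178. Converters are 0.40 − 0.178 = 22.2% and reverters 0.20 − 0.178 = 2.2%. At φ = 0 they are 32% and 12%; at φ = 0.3, 26.1% and 6.1%.

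**Step 2: tests.** Fisher is applied to pre versus post as two groups of n. For McNemar, let m be the number of discordant pairs, k the smaller of converters and reverters, and X binomial(m, ½). Exact p = 2P(X ≤ k). Mid-p = 2P(X ≤ k) − P(X = k).

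**Step 3: power for 20% to 40%, by enumerating every table.**

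| n | φ | Fisher | Exact McNemar | Mid-p McNemar |
|---|---|---|---|---|
| 40 | 0 | 0.41 | 0.40 | 0.48 |
| 40 | 0.3 | 0.39 | 0.53 | 0.62 |
| 40 | 0.5 | 0.37 | 0.69 | 0.79 |
| 25 | 0 | 0.23 | 0.22 | 0.30 |
| 25 | 0.3 | 0.19 | 0.29 | 0.40 |
| 25 | 0.5 | 0.15 | 0.35 | 0.50 |
| 17 | 0 | 0.14 | 0.13 | 0.20 |
| 17 | 0.3 | 0.10 | 0.13 | 0.23 |
| 17 | 0.5 | 0.07 | 0.12 | 0.25 |
| 12 | 0 | 0.09 | 0.06 | 0.12 |
| 12 | 0.3 | 0.06 | 0.04 | 0.11 |
| 12 | 0.5 | 0.04 | 0.03 | 0.09 |

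Other rates at n = 40, φ = 0.5 (Fisher / exact / mid-p): 10% to 30%, 0.53 / 0.83 / 0.92; 30% to 50%, 0.31 / 0.63 / 0.72.

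**Step 4: rejection rate with no change, 20% at both times.** At φ = 0, 0.3 and 0.5, Fisher rejects in 2.8%, 0.9% and 0.24% of trials at n = 40, and in 1.9%, 0.6% and 0.15% at n = 17. Mid-p rejects in 4.4%, 4.0% and 3.3% at n = 40. With negative correlation the direction reverses: at n = 45, 30% responders and φ = −0.3, Fisher rejects in about 6.0% (simulation).

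**Step 5: one worked table, n = 40, responders rising from 8 to 16.** Fisher gives p = 0.087 however many patients revert. Paired intervals use Newcombe's square-and-add method with Wilson limits and continuity-corrected φ.

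| Converters / reverters | Exact McNemar p | Mid-p | Paired 95% CI for the 20-point rise |
|---|---|---|---|
| 8 / 0 | 2/256 = 0.008 | 1/256 = 0.004 | 6.5 to 32.9 |
| 10 / 2 | 158/4096 = 0.039 | 92/4096 = 0.022 | 3.1 to 35.5 |
| 12 / 4 | 5034/65536 = 0.077 | 3214/65536 = 0.049 | 0.3 to 37.8 |

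Treated as independent samples, the interval is −0.1 to 38.1 in every row.

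**Step 6: the cross-table reading.** Take 5 patients positive both times and 15 negative both times, so nobody changes. Fisher on that table gives p = 1/15504 = 0.00006; McNemar gives p = 1.

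**The case against.** **Little rests on this test.** Section 4.3 calls the secondary analyses primarily descriptive, and no error rate or decision rule is attached to the immune comparisons. The listed immune objective is association "with clinical responses in patients who are receiving semi-annual vaccine boosting", and for that 4.3.2 says "Univariate and multivariate modeling will be used quantify the associations", using logistic and Cox models that this point does not affect. Continuous measures are already paired, and plots of change per patient are planned. No dichotomous immune variable is named, so the test may apply to few variables. All of this stands, and it limits the consequence. It does not make the prescribed test right.

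**Comparing Fisher with mid-p mixes two changes**, pairing and a less conservative p-value. This is fair, which is why exact McNemar is shown alongside. At n = 40 and φ = 0.5, pairing alone moves power from 0.37 to 0.69; at n = 25, from 0.15 to 0.35. At n = 17 most of the gain comes from mid-p, and at n = 12 exact McNemar is slightly weaker than Fisher. At φ = 0, pairing alone gains nothing at any size shown.

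**A boost comparison is not a test of first induction**, because patients at their first boost have been vaccinated before. This is true of the boost sentence. However, the antitumor-immunity paragraph takes samples around each vaccination and inherits the same tests, so the link to induction holds there.

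**Mid-p is a preference.** It does not strictly guarantee the 5% level, and exact McNemar would also repair the defect. This stands: the choice is open, the pairing is not.

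**Conclusion.** The concern holds. The plan prescribes an unpaired test for paired categorical data, neither reading of it tests change properly, and no other section corrects it. It should be changed, but it is not critical.

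The size depends on assumed response rates and correlations. With about 25 or more complete pairs and a correlation of 0.3 to 0.5, Fisher gives up substantial power: for 20% to 40% responders, 0.15 to 0.39, against 0.29 to 0.69 for exact McNemar and 0.40 to 0.79 for mid-p. With 17 pairs or fewer, every test is weak and the main benefit is an honest report of who changed. With non-negative correlation the error is loss of power, not extra false positives. The primary safety endpoint, the toxicity stopping rule, the immune–clinical models and the continuous comparisons are unaffected.

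**What to change.** In section 4.3.1, for patients with both samples, replace Fisher's test in the pre/post comparisons with one pre-specified paired test:

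- **Dichotomous variables:** mid-p McNemar at all sample sizes.
- **More than two categories:** Stuart–Maxwell with a within-patient permutation p-value.
- **Report with each test:** number of complete pairs, converters, reverters, and the paired difference in proportions with a 95% confidence interval. Also give the number of patients with only one sample, who drop out of the paired test but can stay in the summaries at each time point.

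The antitumor-immunity measures then inherit the corrected analysis.

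The cost is SAP wording; the data are the same. Over 8 to 45 pairs, the null rejection rate of mid-p was at most 4.75% when no more than half the pairs were discordant, which covers every non-negative correlation. It exceeded 5% only at higher discordance, reaching 7.7% if every pair is discordant. Exact McNemar keeps the level but can be weaker than Fisher with few pairs: for 0 to 5 responders of 17, Fisher gives 0.044, exact McNemar 0.063 and mid-p 0.031. If strict control is preferred, exact McNemar is acceptable.

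An optional clarification: the between-time tests in 4.3.4 are also unpaired, but they are given only as examples, so paired methods are already allowed there and could simply be named.
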